**6.2.4.7. Week 16 Visit**

- 6.2.4.7.1. At 16 week visit, subjects will have vitals taken, pill count will be performed; both the MAAS and HIV-SI will be completed, followed by history, symptom based physical, and laboratory exam. Pill count will be taken from bottle dispensed at baseline visit. Staff will confirm with patient that they have the commercial medication .

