4.2.2.5. Change at 4 months from baseline in absolute and percentage weight

4.2.2.6. Number of drug discontinuation for any reason

4.2.2.7. Compare adherence measured by adherence surveys on week 4 and Week 16 to the pill counts from week 4 and Week 16.

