### 5.2. Packaging and Labeling/Storage and Handling

**5.2.1.** SYMTUZA (darunavir, cobicistat, emtricitabine, and tenofovir alafenamide) tablets are supplied as yellow to yellowish-brown, capsule-shaped, film-coated tablets debossed with “8121” on one side and “JG” on the other side. SYMTUZA is packaged in bottles of 30 tablets (NDC 59676-800-30), with a silica gel desiccant and child-resistant closure.

**5.2.2.** Study drug will be stored at 20°C-25°C (between 68°F-77°F); with excursions permitted to 15°C-30°C (59°F-86°F). • Dispensed in the original container. Container will be tightly closed with desiccant inside to protect from moisture.

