**5.5. Accountability for Study Drug**

**5.5.1.** Subjects will be instructed to bring all study medication in the original container at each clinic visit for drug accountability. The Investigator will be responsible for maintaining accurate records for all study drug bottles dispensed and tablets returned. Study medication supplies, including partially used or empty bottles, must be accounted for by the investigator prior to destruction or return.

**5.5.2.** The Investigator is responsible for ensuring adequate accountability of all used and unused study drug. This included acknowledgement of receipt of each shipment of study drug (quality and condition). All used and unused study drug dispensed to subjects must be returned to the site.

**5.5.3.** Study Drug accountability records will include:

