5.5.3.1. Date received and quantity of IMP kits

5.5.3.2. Date, subject number, subject initials, the IMP kit number dispensed

5.5.3.3. Date, quantity of used and unused IMP returned, along with the initials of the person recording the information.

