**6.2.4.4. Baseline Visit**

- 6.2.4.4.1. If required labs have been performed within 30 days baseline may be performed same day and self-completed HIV Symptom Index (HIV-SI, Appendix 2) survey will be completed, baseline labs will be drawn and patient will be given 30 day supply of study drug.
- 6.2.4.4.2. If baseline is not done same day: vitals will be taken prior to HIV-SI survey being completed. Then updated history and symptom based physical will be performed and baseline labs will be drawn. Patient will be given 30 day supply of study drug; first dose will be taken in office.

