**6.2.4.5. Week 4 Visit**

- 6.2.4.5.1. At 4 week visit, vitals will be taken, pill count will be performed, MAAS and HIV-SI surveys completed. Followed by history, symptom based physical, and laboratory exam. Patient will be given 90-day supply of study drug.

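### The Week 16 pill count is to be taken from the baseline bottle, a 30-day supply that cannot measure adherence from Week 4 to Week 16

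*Protocol*

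**What the plan says.** All references are to the protocol.

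- **Week 16 count (6.2.4.7.1):** "Pill count will be taken from bottle dispensed at baseline visit".
- **Supply at baseline (6.2.4.4):** both baseline routes give 30 days of drug; for a separate baseline visit the text reads "Patient will be given 30 day supply of study drug; first dose will be taken in office".
- **Supply at Week 4 (6.2.4.5):** a pill count is done at this visit, and "Patient will be given 90-day supply of study drug".
- **Bottle size and dosing (5.2.1, 5.3.1):** "SYMTUZA is packaged in bottles of 30 tablets", taken one per day.
- **Schedule (Table 6.2.4.1.2):** drug is dispensed at baseline and Week 4; adherence and accountability are checked at Week 4 and Week 16.
- **Endpoints that use the counts:** 4.2.2.7 reads "Compare adherence measured by adherence surveys on week 4 and Week 16 to the pill counts from week 4 and Week 16". Sections 8.2.2.2.2 and 8.7.1.2 add the percentage of subjects at or above 90% by pill count.
- **Accountability (5.5):** "Subjects will be instructed to bring all study medication in the original container at each clinic visit for drug accountability", and "All used and unused study drug dispensed to subjects must be returned to the site". The records include "Date, quantity of used and unused IMP returned".
- **Commercial supply (6.2.4.6):** a prescription goes to the subject's pharmacy about two weeks before the Week 16 visit.

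**The concern.** The bottle named for Week 16 belongs to the wrong interval. By Week 4 it is nearly used up, and it is the only bottle that could have been counted then. From Week 4 onward the subject takes tablets from a different supply, which the Week 16 sentence leaves out.

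Endpoint 4.2.2.7 pairs survey and pill count separately at Week 4 and Week 16. With the baseline bottle as source, the Week 16 survey would be compared with what is in effect a second reading of the Week 4 count.

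This matters because adherence is the Part 2 primary objective. The primary endpoint is self-reported on the MAAS, whose psychometric properties are themselves to be assessed in Part 1 (8.2.1.2.1). The pill count is the protocol's only direct adherence measure that is not self-report.

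**Working it through.** **Inputs.** One tablet a day (5.3.1); 30 tablets issued at baseline (6.2.4.4, 5.2.1); 90 tablets issued at Week 4 (6.2.4.5); visits at Weeks 4 and 16 (6.2.4.1.2), taken here as days 28 and 112. The protocol gives no figure for this point to reproduce.

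**Coverage of the named bottle.**
- Weeks 4 to 16: 112 − 28 = 84 days, and 84/112 = 75% of follow-up.
- Tablets dispensed: 30 + 90 = 120; the named bottle holds 30/120 = 25% of them.
- A subject who takes every dose to Week 4 has 30 − 28 = 2 tablets left, enough for 2/84 = 2.4% of the later interval.

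**What the bottle would show.** The protocol sets no denominator for the count, so both tablets dispensed (30) and days elapsed to Week 4 (28) are used. Cases (a) and (b) assume that baseline tablets left at Week 4 are not taken later.

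| Subject | Bottle, /30 | Bottle, /28 | True, Weeks 0–16 | True, Weeks 4–16 |
|---|---|---|---|---|
| (a) No dose missed to Week 4, then stops | 28/30 = 93% | 28/28 = 100% | 28/112 = 25% | 0/84 = 0% |
| (b) Misses 4 of the first 28, none after | 24/30 = 80% | 24/28 = 86% | 108/112 = 96% | 84/84 = 100% |

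Case (a) passes the 90% threshold wrongly. Case (b) fails it wrongly.

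**If leftovers are taken first instead.** A subject fully adherent to Week 4 empties the bottle with the next two doses. It then reads 30/30 = 100% whether 0, 10, 42 or 82 of the 84 later doses are missed, that is, for true Week 4–16 adherence of 100%, 88.1%, 50% or 2.4%. Under this assumption case (b) also reads 30/30 = 100%, so its downward error disappears.

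**With the right source.** Full adherence leaves 90 − 84 = 6 tablets of the Week 4 supply if baseline leftovers are not used. Counting everything dispensed, it leaves 120 − 112 = 8. The 90% threshold is then 76 of 84 doses for Weeks 4–16 (0.9 × 84 = 75.6) or 101 of 112 overall (0.9 × 112 = 100.8).

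**The case against.** The strongest reply is that the data are not lost. Section 5.5 has subjects bring all study drug to each visit and return it, returned quantities are recorded, and accountability is scheduled at Week 16. An analyst could rebuild the Week 4–16 count from those records. This is true and limits the harm, but the count that the protocol actually specifies remains the wrong one.

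For the same reason, the sentence does not make compliance with section 5.5 impossible: a site could account for every bottle and still count only one. The sharper conflict is with endpoint 4.2.2.7.

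The sentence may be a misplaced Week 4 instruction, or an attempt to keep study bottles apart from the commercial supply prescribed around Week 14. The document does not say which. On either reading, the wording excludes the Week 4 study bottles.

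The illustrations can also be challenged. Case (a) is extreme, and a subject known to have stopped would fall under the early discontinuation visit. Case (b) depends on leftovers not being taken; if they were handed back at Week 4, its reading is simply the Week 4 count carried forward. Both points stand. The main result does not depend on either case: with leftovers used first, the bottle reads 100% across nearly the whole range of later adherence.

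Finally, the affected endpoints are secondary and descriptive. That bears on priority, not on whether the sentence is wrong.

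**Conclusion.** The concern holds. As written, section 6.2.4.7.1 yields a Week 16 count with almost no information on 84 of the 112 days. The Week 16 half of endpoint 4.2.2.7 cannot be answered from it, and any Week 16 or overall use of the 90% pill-count endpoint would be unreliable. Upward misclassification is possible however leftovers are handled; downward misclassification needs the leftovers to go untaken.

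The conclusion rests on the stated dispensing schedule, once-daily dosing and visits on their nominal days. The primary endpoint, viral load, the Week 4 count and the returned-drug records are not affected. It should be fixed, but it does not threaten the main result of the trial.

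**What to change.** Reconcile 6.2.4.7.1 with 4.2.2.7, 5.5 and 6.2.4.5. Replace the sentence so that the Week 16 count is taken from the study bottles dispensed at Week 4, plus any baseline tablets not returned at that visit, and say that commercial tablets obtained after the Week 14 prescription are kept out of the count.

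The cost is one sentence. Study drug is already brought to each visit, returned quantities are already recorded, and accountability is already on the Week 16 schedule. If subjects have already attended Week 16, check which bottles were counted and, where needed, rebuild the count from the accountability records.

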**6.2.4.8. Early Discontinuation Visit**

- 6.2.4.8.1. If the subject discontinues the study drug prior to the Week 16 Visit, the subject will be asked to return to the clinic within 10 days of stopping study drug for the Early Study Drug Discontinuation Visit. Every attempt should be made to keep the subject in the study and continue to perform the required follow ups and procedures through to the Week 16 Visit. If this is not acceptable to the subject or investigator, the subject may be withdrawn from the study. In the event that the subject is not kept in the study, physical and laboratory exam, as well as the MAAS and HIV-SI should be performed unless the subject does not consent to them.

**6.2.4.9. Post Study Visit**

- 6.2.4.9.1. If any significant abnormality is detected either at 4 month end of study visit or early discontinuation visit, a repeat exam and laboratories will be performed approximately 30 days following (or sooner, if PI believes to be clinically indicated) to ensure their resolution, unless at the determination of the PI they are deemed not related to the study drug.

Table 6.2.4.1.2: Overview of Study Procedures

Procedures	Screening and/or Baseline Combined Visit	Screening (if not same day as screen)	Baseline (if not same day as screen)	Week 4	Week 14 Event	Week 16	Early Discontinuation
Vitals	X	X	X	X		X	X
MAAS	X	X		X		X	X
HIV-SI	X		X	X		X	X
History and Physical	X	X					
History and Symptom based physical			X	X		X	X
Complete Blood Count	X		X	X		X	X
CD4 panel	X		X	X		X	X
Complete Metabolic Panel	X		X	X		X	X
HIV-1 Quantitative viral load	X		X	X		X	X
Urinalysis	X		X	X		X	X
Study Drug Dispensation			X	X			
Treatment Adherence and Accountability				X		X	
Commercial Script sent to Patient's Pharmacy					X		
HIV Genotype	if viral load >200 copies/mL at last check		if viral load >200 copies/mL at last check	if viral load >200 copies/mL at last check		if viral load >200 copies/mL at last check	if viral load >200 copies/mL at last check
Urine pregnancy	if indicated		if indicated	if indicated		if indicated	if indicated
Hepatitis B viral load	if indicated		if indicated	if indicated		if indicated	if indicated

## 7. Safety Data Collection and Reporting

### 7.1. See Appendix 3 (Exhibit B, Safety and Data Reporting)

### 7.2. Clinical Laboratory Abnormalities as Adverse Events

7.2.1.1. Laboratory abnormalities (e.g., clinical chemistry, hematology, and urinalysis) that require medical or surgical intervention or lead to study drug interruption, modification or discontinuation must be recorded as an AE or SAE. In addition, laboratory or other abnormal assessments (e.g., EKG, x-rays, and vital signs) that are associated with signs and/or symptoms must be recorded as an AE or SAE if they meet the definition. If the laboratory abnormality is part of a syndrome, record the syndrome or diagnosis, not the laboratory result (i.e. "anemia," not "decreased hemoglobin").

### 7.3. Assessment of Adverse Events

7.3.1.1. The investigator or qualified sub-investigator is responsible for assessing AEs and SAEs for causality and severity as well as for final review and confirmation of accuracy of event information and assessments.

### 7.4. Assessment of Causality for Study Drugs and Procedures

7.4.1.1. The investigator or qualified sub-investigator is responsible for assessing the relationship to the study drug using clinical judgement and the following considerations:

7.4.1.1.1. **No:** Evidence exists that the adverse event has an etiology other than the study drug. For SAEs, an alternative causality must be provided (e.g., preexisting condition, underlying disease, intercurrent illness, or concomitant medication).

7.4.1.1.2. **Yes:** There is reasonable possibility that the event may have been caused by the study drug.

7.4.1.2. It should be emphasized that ineffective treatment should not be considered as causally related in the context of adverse reporting.

7.4.1.3. The relationship to study procedures (e.g., invasive procedures such as venipuncture) should be assessed using the following considerations:

7.4.1.3.1. **No:** Evidence exists that the adverse event has an etiology other than the study procedure.

7.4.1.3.2. **Yes:** The adverse event occurred as a result of protocol procedures.

### 7.5. Assessment of Severity

7.5.1.1. AE severity should be recorded and graded according to the Grading Scale for Severity of Adverse Events and laboratory Abnormalities (Appendix 4). For AE associated with laboratory abnormalities, the event should be graded on the basis of the clinical severity in the context of the underlying conditions; which might not be in agreement with the grading of the laboratory abnormality.

7.5.1.2. The distinction between the seriousness and the severity of an AE should be noted. Severe is a measure of intensity; a severe reaction is not necessarily a serious reaction. For example, a subject might have a headache that is described as severe, but would not be considered a SAE unless it met one of the criteria for serious events.

### 7.6. Toxicity Management

7.6.1. All clinical events and clinically significant laboratory toxicities will be managed according to uniform guidelines detailed in Appendix 3 and as outlined below.

7.6.1.1. Clinical events and clinically significant laboratory abnormalities will be graded according to the Grading Scale for Severity of Adverse Events and laboratory Abnormalities (Appendix 4).

7.6.1.2. Grade 3 and 4 clinically significant laboratory abnormalities should be confirmed by repeat testing within 5 calendar days of receiving results and before study drug discontinuation, unless such a delay is not consistent with good medical practice.

7.6.1.3. Any questions regarding toxicity management should be directed to the Investigator.

#### **7.6.2. Grades 1 and 2 Clinical Event or Laboratory Abnormality**

7.6.2.1. Continue study drug at the discretion of the Investigator

#### **7.6.3. Grade 3 Clinical Event or Laboratory Abnormality**

7.6.3.1. For Grade 3 clinical event or clinically significant laboratory abnormality, study drug may be continued if the event is considered to be unrelated to study drug.

7.6.3.2. For a Grade 3 clinical event or clinically significant laboratory abnormality confirmed by repeat testing that is considered to be related to the study drug, study drug will be withheld until the toxicity returns to  $\leq$  grade 2. When restarting study drug following resolution of the adverse event, the study drug should be restarted at full dose.

7.6.3.3. If following re-challenge with study drug a laboratory abnormality returns to  $\geq$  Grade 3 and is considered to be related to the study drug, then the study drug will be permanently discontinued and the subject managed according to local practice. Recurrence of laboratory abnormalities considered unrelated to the study drug may not require permanent discontinuation.

#### **7.6.4. Grade 4 Clinical Events or Laboratory Abnormality**

7.6.4.1. For a Grade 4 clinical event or clinically significant laboratory abnormality confirmed by repeat testing that is considered to be related to the study drug, the study drug will be permanently discontinued and the subject managed according to local practice. The subject should be followed as clinically indicated until the laboratory abnormality returns to baseline or is otherwise explained, whichever occurs first.

7.6.4.2. A clinically significant Grade 4 laboratory abnormality that is not confirmed by repeat testing should be managed according to the algorithm for the new toxicity grade.

7.6.4.3. Study drug may be continued without dose interruption for a clinically non-significant Grade 4 laboratory abnormality (e.g., elevated CK after significant exercise or triglyceride elevation on a non-fasting specimen) or a clinical event considered unrelated to the study drug, but must be discussed with the Investigator.

#### **7.6.5. ALT Flare**

7.6.5.1. Defined as: serum ALT  $> 10 \times$  upper limit of normal (ULN) and  $> 2$  times baseline value, confirmed with repeat testing within 7 days of original results receipt, with or without associated symptoms

##### **7.6.5.2. Management of ALT Flare**

7.6.5.2.1. When initial results are received, schedule subject to return to the clinic as soon as possible (ideally within 3 days of initial blood draw). During the visit, in addition to redrawing blood for repeat CMP testing, clinical assessment of the subject will be performed. The assessment should include a physical examination and evaluation of the subject's mental status.

7.6.5.2.2. If ALT elevation is confirmed, the following labs should be performed: plasma HBV DNA, HBV serology (HBsAg and HBsAb), HAC IgM, HCV serology, quantitative HDV RNA.

7.6.5.2.3. Based on the results of the confirmatory tests, the following treatment modifications are recommended:

7.6.5.2.3.1. Elevated liver enzymes, normal or stable total bilirubin relative to baseline

7.6.5.2.3.1.1. If ALT levels are elevated (as specified in 7.7.5.1) with normal or stable total bilirubin, the subject may remain on the study drug and should be monitored weekly until ALT levels return to normal or Baseline level. During monitoring, if the ALT values remain persistently elevated, the Investigator will determine whether the study drug should be discontinued.

7.6.5.2.3.2. Elevated liver enzymes, elevated total bilirubin

7.6.5.2.3.2.1. If ALT levels are elevated (as specified in 7.7.5.1) and total bilirubin is confirmed to be  $\geq 2 \times$  Day 1 value and is  $>$  ULN, the investigator should

consider discontinuing the study drug. The subject should be monitored weekly until ALT and total bilirubin levels return to normal or Day 1 level.

7.6.5.2.3.3. During monitoring, if the ALT values and the liver function tests remain persistently elevated, the Investigator should consider discontinuing the study drug.

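### For a confirmed, clinically significant and drug-related ALT flare, section 7.6.4.1 requires permanent discontinuation while section 7.6.5.2.3 sets a weaker standard, and the protocol does not say which governs

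*Protocol*

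**What the plan says.** Two parts of protocol section 7.6 address a very high ALT.

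**General Grade 4 rule.** Section 7.6.4.1 governs Grade 4 findings, both clinical events and laboratory values of clinical significance. Where such a finding is "confirmed by repeat testing that is considered to be related to the study drug, the study drug will be permanently discontinued". Section 7.6.4.3 gives the exception for laboratory values: "Study drug may be continued without dose interruption for a clinically non-significant Grade 4 laboratory abnormality".

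**ALT flare rule.** Section 7.6.5.1 defines a flare as ALT above 10 x ULN and above twice baseline, "confirmed with repeat testing within 7 days of original results receipt, with or without associated symptoms". Section 7.6.5.2 then sets out recall, viral hepatitis work-up, action and monitoring. The actions are introduced with the words "the following treatment modifications are recommended" and divide by bilirubin:

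- Section 7.6.5.2.3.1.1: "with normal or stable total bilirubin, the subject may remain on the study drug", with weekly monitoring. If ALT stays high, the Investigator decides about stopping.
- Section 7.6.5.2.3.2.1, for bilirubin at least 2 x Day 1 and above ULN, tells the investigator to "consider discontinuing the study drug. The subject should be monitored weekly until ALT and total bilirubin levels return to normal"; a return to the Day 1 value also ends the monitoring.

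Appendix 4 grades ALT above 10 x ULN as Grade 4.

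**The concern.** The two rules apply to the same laboratory event but differ in force. One removes discretion once the rise is judged clinically significant and related. The other leaves discretion in place and never asks about relatedness. An investigator who keeps dosing a subject with a drug-related ALT above 10 x ULN could cite the more specific section in support, while section 7.6.4.1 would call the same decision a departure from the protocol.

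Subject safety is what is chiefly at stake. The effect on the statistics is small. Number of drug discontinuations is a secondary endpoint (sections 4.2.2.6 and 8.7.1.7), and whether such a subject is stopped feeds directly into that count.

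**Working it through.** The protocol states no figure to reproduce. The check is whether the two rules cover the same subjects, and then whether they lead to the same action.

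**1. Does every flare meet Grade 4?** The Appendix 4 Grade 4 ALT threshold is above 10 x ULN. The first limb of the flare definition in 7.6.5.1 is also above 10 x ULN, and the definition requires confirmation by repeat test, as 7.6.4.1 does. Every flare is therefore a confirmed Grade 4 ALT.

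**2. Does the twice-baseline limb separate the two sets?** It makes a flare narrower than Grade 4 only when 2 x baseline reaches 10 x ULN, that is, when baseline is 10 / 2 = 5 x ULN or more. Section 6.2.3.1.3 limits entry ALT to 3 x ULN, and 2 x 3 = 6 x ULN, which is below 10. If the baseline value also respects the entry limit, the two sets coincide. That is an assumption: under 6.2.4.3.2 and 6.2.4.4.1 the eligibility tests can predate the baseline draw. Step 1 does not depend on it.

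**3. What action follows if the flare is clinically significant and related?**

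- Under 7.6.4.1: permanent discontinuation, whatever the bilirubin. The exception in 7.6.4.3 does not apply, because the abnormality is clinically significant.
- Under 7.6.5.2.3.1.1 (bilirubin normal or stable): continuation is allowed. This is where the two sections diverge most.
- Under 7.6.5.2.3.2.1 (bilirubin at least 2 x Day 1 and above ULN): discontinuation is to be considered. This is a weaker standard than 7.6.4.1 rather than its opposite.

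A bilirubin that has risen but is below 2 x Day 1 fits neither branch clearly.

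**4. Does any other text settle precedence?**

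- 7.6.1 applies Appendix 3 and the rules that follow it together, without ranking them. Appendix 3 concerns safety reporting and has no ALT stopping rule.
- 7.6.1.3 says "Any questions regarding toxicity management should be directed to the Investigator", which returns the question to the person who needs the rule.
- 7.6.6 covers work-up of hepatobiliary toxicity.
- 7.7.1 requires stopping for unacceptable toxicity but does not define it.
- The one internal reference in the flare branches is to 7.7.5.1, which does not exist. The definition is in 7.6.5.1.

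None of these says which section governs.

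**The case against.** The strongest reply is that nothing has to be broken. Section 7.6.4.1 is mandatory, whereas the flare branches are recommendations. Stopping a significant, related case complies with both sections, and being told to consider stopping is compatible with a duty to stop. On this view the mandatory rule simply prevails.

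A second reply is that 7.6.5 governs the interim. It orders viral hepatitis tests and bases its recommendations on the confirmatory results, so it can be read as managing the subject until the cause is known, after which 7.6.4.1 takes over. The missing causality condition would then be expected.

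A third is practical. Part 2 recruits from one clinical site, the investigator or a qualified sub-investigator judges causality, and the Investigator takes toxicity questions and decides on stopping. There is little room for different teams to apply different readings.

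Much of this stands. It rules out calling the sections a strict logical contradiction, and it limits the exposure. It does not remove the gap. Both harmonising readings are plausible, but the protocol states neither. The flare definition is not restricted by cause, and the branches turn on bilirubin rather than on the viral results. Section 7.6.5 is also a complete pathway of its own, so it can equally be read as displacing the general rule.

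A reader might go further and infer that the plan treats worse toxicity more leniently. A related, clinically significant, confirmed ALT of 8 x ULN is Grade 3, and under 7.6.3.2, once it is "considered to be related to the study drug, study drug will be withheld until the toxicity returns to" Grade 2 or below, whereas 12 x ULN could continue if bilirubin is stable. That inversion follows only if 7.6.5 overrides 7.6.4.1, and the documents do not say that it does.

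**Conclusion.** The point holds as an unresolved inconsistency in a hepatic stopping rule. It is confined to flares that are both clinically significant and judged related. It is sharpest when bilirubin is normal or stable; when bilirubin is clearly raised, the flare section is weaker than 7.6.4.1 rather than opposed to it.

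The primary endpoint, its analysis and the sample size are unaffected. The secondary count of drug discontinuations could change by one for each affected subject, which against the target of 30 is 1 / 30 = 3.3% of enrolment. That endpoint is descriptive and no hypothesis is tested on it. The documents give no rate for ALT above 10 x ULN, so no expected number of cases can be stated.

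A reader might infer that the protocol instructs investigators to keep dosing through drug-induced liver injury. The text does not support that: the flare branches permit and recommend but do not require continuation, and 7.6.4.1 and 7.7.1 remain in force. The clarification should still be made, because the rule concerns subject safety and the correction is very small. The conclusion rests on the Appendix 4 threshold and the wording of 7.6.4 and 7.6.5. Only the statement that flares and confirmed Grade 4 ALT are the same set needs the further assumption that baseline ALT meets the entry limit.

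**What to change.** At the start of section 7.6.5.2.3, add: *If the ALT rise is judged clinically significant and related to study drug, 7.6.4.1 governs and study drug is permanently discontinued; the recommendations below apply to all other ALT flares.*

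As a clerical edit, change the cross-reference 7.7.5.1 to 7.6.5.1 in both flare branches. The confirmation windows need no change, since a repeat within the 5 days of 7.6.1.2 also meets the 7-day limit of 7.6.5.1.

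The cost is one sentence and a corrected reference, submitted as a protocol modification for IRB approval under section 9.14. No visit, test or sample size changes.
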